### 14.3.3 Exposure and treatment compliance

Exposure to treatment will be presented for the safety analysis set as days of exposure per treatment group.

Adherence to treatment regimen will be recorded in the eCRF. If any complications or deviations in administration are observed, these will be described as protocol deviations. Adherence will be presented for the safety analysis set for each treatment group.

[figure not shown]
### 14.3.4 Multiple testing procedure

The primary and secondary endpoints will be evaluated hierarchically in the order shown in [Panel 13](#).

The hypothesis relating to a specific endpoint cannot be rejected unless all hypotheses relating to endpoints earlier in the hierarchy are also rejected.

**Panel 13: Testing procedure for primary and secondary endpoints**

EASI, Eczema Area and Severity Index; EASI75, at least 75% reduction in EASI score; IGA, Investigator’s Global Assessment.

Non-inferiority hypothesis to be tested for the primary endpoints:  $H_0: \pi_{\text{tralo}} - \pi_{\text{placebo}} \leq -25\%$  versus  $H_1: \pi_{\text{tralo}} - \pi_{\text{placebo}} > -25\%$ ,

Superiority hypothesis to be tested for the secondary endpoints:  $H_0: \pi_{\text{tralo}} - \pi_{\text{placebo}} \leq 0\%$  versus  $H_1: \pi_{\text{tralo}} - \pi_{\text{placebo}} > 0\%$ ,

where  $\pi_{\text{tralo}}$  and  $\pi_{\text{placebo}}$  denotes the response rate with tralokinumab and placebo, respectively.

All hypotheses will be tested at a one-sided 2.5% significance level. For the non-inferiority hypotheses, the null hypothesis will be rejected if the two-sided 95% CI for the difference in immune response rate lies entirely to the right of the non-inferiority limit (-25%). For the superiority hypotheses, a two-sided 95% CI for the difference in response rates and a corresponding two-sided p-value will be calculated; the null hypothesis will be rejected if the p-value is smaller than 5% and the point estimate is in favour of the alternative hypothesis (that is, greater than 0).

### 14.3.5 Analysis of primary endpoints

Positive anti-tetanus response at Week 16 (3-fold IgG increase compared to Week 12 if  $\text{IgG} \leq 1.0$  IU/mL at Week 12; or  $\text{IgG} \geq 2.5$  IU/mL if  $\text{IgG} > 1.0$  IU/mL at Week 12) and positive anti-meningococcal response at Week 16 ( $\text{IgG} \geq 3.0$  mcg/mL with at least a 3-fold increase compared to Week 12) are binary endpoints. The difference in response rates between treatment groups will be calculated using the Mantel-Haenszel estimate of the risk difference stratified by baseline disease severity (IGA 3 or 4) together with the 95% CI. Non-inferiority of tralokinumab will be demonstrated if the lower limit of the 95% CI is greater than -25%.

The primary endpoints will be analysed for FAS and the per protocol set; the per protocol analysis will be considered the primary analysis. Analyses will be based on observed data; hence, missing data will not be imputed.

### 14.3.6 Analysis of secondary endpoints

#### 14.3.6.1 Overview of estimand framework

Three estimands addressing different aspects of the trial objectives will be defined:

- Primary estimand: ‘composite’.
- Secondary estimand: ‘hypothetical’.
- Tertiary estimand: ‘treatment policy’.

The applied estimands incorporate 2 main types of events that influence how the treatment effects are estimated:

- **Initiation of rescue medication:** Some of the estimands use the initiation of rescue medication as an event that modifies the applied value of an endpoint, e.g. by defining a subject receiving rescue medication as a non-responder.
- **Permanent discontinuation of IMP:** This event occurs when a subject is permanently withdrawn from the treatment or the trial as described in Section 10.3. This can either happen at his/her own initiative or at the investigator’s discretion. The event also includes the possibility of a subject being lost to follow-up. The timing of the event is defined as the date of the early termination visit for withdrawn subjects or – in the case of a subject lost to follow-up – the date of the last known visit to the clinic. As for the rescue medication, the event type is used to modify an applied endpoint value.

All analyses will be based on the FAS unless otherwise specified.

### 14.3.6.2 Primary estimand: ‘composite’

The primary estimand for the first 2 secondary endpoints will be:

- Treatment difference in response rates of IGA 0/1 and EASI75 after 16 weeks achieved without rescue medication, regardless of treatment discontinuation.

The primary estimand assesses the expected difference in response rates (defined as response obtained without initiation of any rescue medication) after 16 weeks, resulting from initiation of a treatment regimen with tralokinumab compared to a treatment regimen with placebo.

#### Primary analysis for the primary estimand

Data retrieved at Week 16 for subjects who have permanently discontinued IMP prior to Week 16 will be included in the analysis. Subjects who prior to the Week 16 visit have received rescue medication will be considered non-responders, reflecting an assumption that initiation of rescue medication indicates failure of the randomised treatment to achieve response, and that a (possible) observed positive response after initiation of rescue medication is not attributable to the randomised treatment. Missing data for subjects who did not attend the Week 16 visit and where rescue medication has not been used prior to Week 16, will be imputed as non-responders.

The difference in response rates between treatment groups will be analysed using the Cochran-Mantel-Haenszel test stratified by baseline disease severity (IGA 3 or 4). The treatment estimate and the corresponding 95% CI will be presented. The null hypothesis of no difference in response rates between tralokinumab and placebo will be tested against the 2-sided alternative that there is a difference.

#### Sensitivity analyses for the primary estimand

Two sensitivity analyses are specified for the primary estimand. In both cases the same Cochran-Mantel-Haenszel test as used for the primary analysis will be applied including stratification by baseline disease severity.

The purpose of the analyses is to assess the robustness of results of the primary analysis with respect to the retrieved data at Week 16 and assumptions regarding missing Week 16 data.

Sensitivity analysis 1: All subjects who have permanently discontinued IMP prior to Week 16 will be imputed as non-responders, even if no rescue medication has been used. This is to reflect a situation where retrieved efficacy data and concomitant medications could be registered less accurately for subjects who have discontinued treatment.

**Sensitivity analysis 2:** Rather than imputing all subjects who do not attend the Week 16 visit and where rescue medication has not been used as non-responders, the following approach will be applied. If subjects have withdrawn due to an AE or due to lack of efficacy, they are still considered non-responders. Data missing for other reasons will be imputed using LOCF, hereby assuming that the last value is a more reliable estimate of the missing response (than a non-response).

### Supplementary analysis

The primary analysis of the primary estimand is repeated based on the per protocol analysis set.

#### 14.3.6.3 Secondary estimand: ‘hypothetical’

The secondary estimand for the first 2 secondary endpoints will be:

- Treatment difference in response rates of IGA 0/1 and EASI75 after 16 weeks if all subjects adhered to the treatment regimen in the sense that they did not discontinue IMP permanently and no rescue medication was made available before Week 16.

The secondary estimand assesses the expected difference in response rates achieved when adhering to the treatment regimen tralokinumab with no rescue medication as compared to a treatment regimen with placebo with no rescue medication.

#### Primary analysis of the secondary estimand

Data collected after permanent discontinuation of IMP or after initiation of rescue medication will not be applied in the analysis.

#### IGA 0/1 responder imputation

Imputation of missing binary IGA 0/1 data at Week 16 will be done using multiple imputations of the underlying 5-point IGA values within the 2 groups defined according to randomised treatment arm assuming that data is missing at random within each arm.

1. In each group, intermittent missing values will be imputed using LOCF to obtain a monotone missing data pattern.
2. An ordinal logistic regression model assuming proportional odds will be fitted to the IGA value at Week 2. The model will include baseline disease severity (IGA 3 or 4) as factor. The estimated parameters, and their variances, will be used to impute missing IGA values at Week 2. 100 copies of the dataset will be generated (seed=13827641).

3. For each of the 100 copies of the dataset, missing values at Week 4 will be imputed in the same way as for Week 2. The imputations will be based on a proportional odds logistic regression model with effects of baseline disease severity (IGA 3 or 4) together with the IGA value at Week 2 as factors. The estimated parameters, and their variances, will be used to impute missing values at Week 4.
4. This stepwise procedure will then be repeated sequentially for Week 6, 8, 10, 12, 14, and 16 with the modification that only the IGA values from the 2 preceding visits will be included as factors in addition to baseline disease severity. The missing binary IGA 0/1 response at Week 16 will be derived from the corresponding underlying imputed IGA value.

### **EASI75 responder imputation**

Imputation of missing binary EASI75 data at Week 16 will be done using multiple imputations of the underlying 72-point EASI values within the 2 groups defined according to randomised treatment arm assuming that data is missing at random within each arm.

1. Intermittent missing values will be imputed in each group using a Markov Chain Monte Carlo method to obtain a monotone missing data pattern and 100 copies of the dataset will be generated (seed=45624941).
2. An ANCOVA model is fitted to the EASI value at Week 2. The model will include effects of baseline EASI as a covariate, and baseline disease severity (IGA 3 or 4) as a factor. The estimated parameters, and their variances, will be used to impute missing EASI values at Week 2. 100 copies of the dataset will be generated (seed=11109941).
3. For each of the 100 copies of the dataset, missing EASI values at Week 4 will be imputed in the same way as for Week 2. The imputations will be based on the same ANCOVA model with effects of baseline EASI as a covariate, and baseline disease severity (IGA 3 or 4) as a factor together with the EASI value at Week 2 as covariate. The estimated parameters, and their variances, will be used to impute missing values at Week 4.
4. This stepwise procedure will then be repeated sequentially for Week 6, 8, 10, 12, 14, and 16 with the modification that only the EASI values from the preceding 2 visits will be included as covariates in addition to baseline EASI as a covariate and baseline disease severity as a factor. The missing binary EASI75 response at Week 16 will be derived from the corresponding underlying imputed EASI value.

### **Analysis of Week 16 response**

For each of the 100 complete data sets, the difference in response rates (either the IGA 0/1 or the EASI75) between treatment groups will be analysed using the Cochran-Mantel-Haenszel

test stratified by baseline disease severity (IGA 3 or 4). The estimates and standard errors from the 100 analyses will be pooled to one estimated treatment difference and associated standard error using Rubin's rule to draw inference. From these pooled estimates, the 95% CI for the treatment difference will be calculated.

### **Sensitivity analysis for the secondary estimand**

Rather than assuming that observations are missing at random within each treatment arm, it is assumed that missing data from subjects who discontinue IMP permanently/receive rescue medication in the tralokinumab arm will resemble missing data from subjects from the placebo arm who do not discontinue IMP permanently/receive rescue medication. The underlying assumption is that the effect of tralokinumab following rescue medication or permanent treatment discontinuation is similar to the effect of placebo. It should be noticed that this assumption is pronouncedly conservative in favour of placebo as it tends to minimise the differences between arms.

Imputation of missing data at Week 16 will be done using a pattern mixture model where missing data in the tralokinumab arm as well as the placebo arm will be imputed from observed data in the placebo arm (using a so-called copy-reference approach). With this exemption, the stepwise multiple imputation procedure and subsequent analysis will be conducted in the same way as specified for the primary analysis of the secondary estimand.

### **14.3.6.4 Tertiary estimand: 'treatment policy'**

The tertiary estimand for the first 2 secondary endpoints will be:

- Treatment difference in response rate after 16 weeks between tralokinumab and placebo, regardless of rescue medication and treatment discontinuation.

The tertiary estimand assesses the average difference in response rates, resulting from initiation of a treatment regimen with tralokinumab and additional rescue medication as compared to a treatment regimen with placebo and additional rescue medication.

### **Primary analysis for the tertiary estimand**

Data retrieved at Week 16 for subjects who have permanently discontinued treatment prior to Week 16 will be included in the analysis.

Imputation of missing data at Week 16 will be done using multiple imputations within 4 groups defined according to randomised treatment arm and whether or not subjects have permanently discontinued IMP prior to Week 16. Within a given treatment arm, retrieved data from discontinued subjects will be used to impute missing data for other discontinued

subjects. Similarly, the available data from not discontinued subjects will be used to impute data for such patients where the Week 16 value is missing.

For not discontinued subjects, the stepwise multiple imputations procedure will be conducted in the same way as specified for the primary analysis of the secondary estimand.

For discontinued subjects, it is expected that the number of subjects with retrieved data at Week 16 will be too small to facilitate the same imputation model as mentioned above. Consequently, an imputation model with only baseline effects (IGA as a factor and EASI as a covariate [only for EASI75]) will be applied for discontinued subjects. Some factors may have to be omitted, depending on the observed data, e.g. if retrieved subjects all have the same baseline severity.

The imputed datasets will be analysed in the same way as specified for the primary analysis of the secondary estimand.

### **Sensitivity analyses for the tertiary estimand**

Rather than imputing Week 16 data as described in the primary analysis of the tertiary estimand, missing observations will be imputed as non-responders. The assumption reflects that discontinued subjects without retrieved data at Week 16 are more likely to be non-responders than resembling discontinued subjects with retrieved data at Week 16.

### **14.3.7 Analysis of other endpoints**

To support the secondary endpoints, EASI50 at Week 16, EASI90 at Week 16, SCORAD75 at Week 16, and SCORAD50 at Week 16 will be analysed and presented for the FAS. These 4 endpoints will be analysed as described for the primary analysis of the primary estimand for the secondary efficacy endpoints.

The change from baseline to Week 16 in EASI, SCORAD, DLQI, EQ-5D-5L, POEM, and HADS will be analysed using a repeated measurements model on the post baseline responses up to Week 16 with an unstructured covariance matrix, Kenward-Roger approximation to estimate denominator degrees of freedom, and the mean modelled as follows (shown for change from baseline in SCORAD):

Change from baseline in SCORAD

$$= \text{treatment} \times \text{visit} + \text{baseline SCORAD} \times \text{visit} + \text{baseline IGA}$$

This model assumes that data is missing at random within each treatment arm. The estimates will be presented with nominal p-values and 95% CI at each visit. Data collected after permanent discontinuation of IMP or after initiation of rescue medication will not be included in the analysis. All analyses will be based on the FAS.

### **14.3.8 Analysis of safety**

The analyses of safety will be based on the safety analysis sets.

#### **14.3.8.1 Adverse events**

AEs will be coded during the course of the trial according to Medical Dictionary for Regulatory Activities (MedDRA). AEs will be presented by preferred terms and primary system organ class (SOC).

Treatment-emergent AEs will be summarised, however, all AEs recorded during the course of the trial will be included in the subject data listings. An event will be considered treatment-emergent if started after the first use of IMP or if started before the first use of IMP (applicable if subject had a wash-out) and worsened in severity thereafter. The tabulations described in the following will only include the treatment-emergent events. In each of the tabulations, AEs will be defined by MedDRA preferred terms within primary SOC.

An overall summary of the number of treatment-emergent AEs, number (percentage) of subjects with any treatment-emergent AEs, SAEs, deaths, premature discontinuations from the trial due to AEs, treatment-related AEs and severe AEs will be presented.

The number of AEs and the number of subjects experiencing each type of AE will be tabulated by treatment group. The percentage of subjects with AEs will be compared between treatment groups by a chi-square test or Fisher's exact test (if expected cell count < 5).

The severity for each type of AE will be tabulated by treatment group.

The causal relationship to IMP (tralokinumab/placebo) for each type of AE will be tabulated by treatment group. Related AEs are defined as AEs for which the investigator has not described the causal relationship to IMP as 'not related'. The number of related AEs and the number of subjects experiencing each type of related AE will be tabulated. The percentage of subjects with related AEs will be compared between treatment groups by a chi-square test or Fisher's exact test (if expected cell count <5).

The causal relationship to IMP (each vaccine) for each type of AE will be tabulated by treatment group. Related AEs are defined as AEs for which the investigator has not described the causal relationship to IMP as 'not related'. The number of related AEs and the number of subjects experiencing each type of related AE will be tabulated. The percentage of subjects with related AEs will be compared between treatment groups by a chi-square test or Fisher's exact test (if expected cell count <5).

SAEs and AESIs will be evaluated separately and a narrative for each will be given. AEs leading to withdrawal from trial will be listed.

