**Panel 2: Schedule of trial procedures (continued)**

Visit	Screening		Treatment period									Follow-up 			Uns. visit  (if appl.)	Early term.  (if appl.)	Nominal Week 16 visit  (if appl.)	References (protocol section)
	1 	2	3	4	5	6	7	8	9	10	11 	12 	13 	14 			11x	
Week	-6	-2	0	2	4	6	8	10	12	14	16	20	24	30			16	
Visit window (days) 	±3	-3	NA	±3	±3	±3	±3	±3	±3	±3	±3	±3	±3	±3	NA	NA	±3	
Investigator assessments of safety																		
Vital signs	X		X 	X 	X 	X	X	X	X	X	X			X	X 	X		11.4.1
Physical examination	X		X				X				X			X	X 	X		11.4.2
ECG	X		X								X			X	X 	X		11.4.3
Chemistry, haematology, IgE (central laboratory)	X 		X		X		X		X		X			X	X 	X		11.4.5
Serum pregnancy test; hepatitis B, C; HIV (central laboratory)	X																	11.4.4; 11.4.5
Urine pregnancy test			X		X		X		X		X			X	X 	X		11.4.4
Urinalysis	X		X		X		X		X		X			X	X 	X		11.4.5
Anti-drug antibodies			X		X						X			X	X 	X		11.4.6
Pharmacokinetics					X						X			X	X 	X		11.6
Adverse events	X	X	X	X	X	X	X	X	X	X	X	X	X	X	X 	X	X	13
Assessment of vaccine antibody response																		
Anti-tetanus response									X		X				X 	X 	X 	11.5
Anti-meningococcal response									X		X				X 	X 	X 	11.5

- 1) For subjects who do not require a wash-out, visits 1 and 2 will be combined and screening will be reduced to 2 weeks; hence, these subjects will only attend visit 2 (Week -2) which will include all assessments shown under Week -6. Similarly, for subjects who only require a 2-week wash-out, screening visits 1 and 2 will be combined (Week -2). The screening period has a maximum duration of 6 weeks.
- 2) Eligible subjects may roll over to the ECZTEND trial at Week 16 or later. See also footnote no. 5.
- 3) All subjects, except for those who roll over to the ECZTEND trial (LP0162-1337), will have a full 14-week off-treatment safety follow-up period. The safety follow-up period includes 2 telephone contacts and an office visit (end-of-trial visit) at Week 30. Subjects may transfer to the ECZTEND trial at any time during the safety follow-up period.
- 4) Visit will be conducted as a telephone contact.

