### **Long-term extension trial**

Eligible subjects may be invited to enter an open-label, long-term extension trial conducted under a separate protocol (LP0162-1337, ECZTEND). Subjects who fulfil the eligibility criteria in the ECZTEND protocol can enter the trial at the Week 16 visit or up to 16 weeks after the last IMP injection in the present trial. Subjects who transfer to ECZTEND must have had their Week 16 visit under the current protocol (LP0162-1341).

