## **7.3 End of trial definition**

A subject is considered to have completed the trial if they have completed all periods of the trial including the safety follow-up visit (Week 30) or if they have transferred to the ECZTEND trial (Section 7.1).

The end of the trial is defined as the date of the last visit of the last subject in the trial globally.

Final collection of data for the primary endpoints will occur at Week 16.

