### 13.2 Collection of adverse event reports

AEs must be collected from time of first trial-related activity after the subject has signed the informed consent form (ICF) until completion of the clinical trial (defined as per [Section 7.3](#)).

AEs must be assessed by medically qualified personnel.

At all visits, the subject will be asked a non-leading question by the investigator about AEs, for example: “How have you felt since I saw you last?” No specific symptoms should be asked for. It is important that the investigator also observes the subject for any changes not reported by the subject and records these changes.

Refer to [Sections 11.4.1](#) to [11.4.5](#) for principles for data entry in the eCRF.

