The safety analysis set comprises all subjects randomised to treatment who were exposed to IMP. The protocol further specifies to exclude subjects from the safety analysis set for whom no post-baseline safety data are available. However, since all subjects receive the first dose of IMP in connection with the Week 0 visit and are subsequently monitored for immediate drug reactions, all exposed subjects are considered to have post-baseline safety data available and no such further exclusions will be made.

In addition to the analysis sets defined in the protocol, a safety follow-up analysis set will be used as the basis for evaluation of adverse events during the safety follow-up period. It comprises all subjects for whom date of last contact is after the date of exposure end, where exposure end is defined as the Week 16 visit for subjects completing the treatment period, and otherwise the date of permanent discontinuation of IMP (tralokinumab/placebo) for subjects not completing the treatment period. See also Section 6.9.2 for further details.

For analysis of efficacy, subjects will be included 'as randomised'.

For analysis of safety, if a subject is mistakenly given an IMP other than that to which they were randomised, they will be analysed 'as treated', thus included in the group according to the therapy actually received by the subject. The below rules will be applied.

Subjects who received at least one dose of tralokinumab will be analysed in the tralokinumab treatment group. Although this may dilute the AE rate in the tralokinumab treatment group slightly by including in the denominator subjects who only received one dose of active treatment, it will ensure that no significant drug reactions to tralokinumab will erroneously be assigned to placebo.

The definition of the per protocol analysis set as described in the protocol has been updated to accept negligible deviations in baseline disease severity related to the EASI status. Thus, the criteria from inclusion criterion 7 have been modified to require an EASI score of ≥ 12 at screening OR ≥ 16 at baseline instead of requiring both criteria to be met. The rationale for this change is that marginal deviations in baseline disease severity is not considered to affect the vaccine response.

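### Follow-up AEs have no time-at-risk denominator, although subjects may leave for the extension at any time in Weeks 16-30, and the SAP does not say whether the AE test covers them

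*Protocol*

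**What the plan says.** **Length of follow-up.** Under Panel 2, footnote 3 of the protocol, subjects who do not roll over "will have a full 14-week off-treatment safety follow-up period". The same footnote adds: "Subjects may transfer to the ECZTEND trial at any time during the safety follow-up period". Protocol Section 7.1 gives the window: eligible subjects "can enter the trial at the Week 16 visit or up to 16 weeks after the last IMP injection in the present trial". The last injection is at Week 14, so the window runs from Week 16 to Week 14 + 16 = Week 30.

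**End of AE observation.** Protocol Section 13.2 collects AEs until trial completion as defined in Section 7.3. Under that section a subject has completed after the Week 30 visit "or if they have transferred to the ECZTEND trial". Read at subject level, transfer ends AE collection in this trial.

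**Comparison of AEs.** Protocol Section 14.3.8.1 says: "The percentage of subjects with AEs will be compared between treatment groups by a chi-square test", with Fisher's exact test for low expected counts. Its tabulations cover treatment-emergent events: "An event will be considered treatment-emergent if started after the first use of IMP", or if they worsened after it. No end is given.

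**SAP additions.** SAP Section 5 says that "a safety follow-up analysis set will be used as the basis for evaluation of adverse events during the safety follow-up period". Membership requires only a last contact later than exposure end. SAP Section 6.8.1 assigns AEs to the treatment or follow-up period and otherwise says only that they are summarised and listed. SAP Section 6.5 defines patient-years from the exposure time of Section 6.9.2, which ends at the Week 16 visit or at permanent discontinuation of IMP.

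**The concern.** A subject seen for a few days after Week 16 and one seen for the full 14 weeks each count as one in the follow-up denominator. The percentage with an AE rises with time observed, so an arm followed for longer will show more AEs at the same underlying risk.

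A link between arm and transfer time is plausible. Follow-up is off treatment, the extension is open-label, and the sample size section expects different disease control at Week 16 (IGA 0/1 30% versus 10%, EASI75 40% versus 15%). If disease control affects when subjects transfer, follow-up length will depend on arm. The bias could go either way: poorly controlled subjects might leave sooner to obtain treatment, or responders might leave sooner to keep it.

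At stake is the reading of the off-treatment safety table, and of any Week 0-30 AE table built on the open-ended protocol definition.

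**Working it through.** The documents give no transfer rate, follow-up duration by arm or AE rate, so there is no planned figure to reproduce. The calculation below only illustrates the mechanism.

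**From the documents:** 14 weeks of planned follow-up; transfer possible from Week 16 to Week 30; 200 subjects randomised 1:1, so 100 per arm; subjects with no contact after exposure end are left out of the follow-up set.

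**Assumed:** the same constant AE hazard in both arms, with 30% of subjects having an AE in a full 14 weeks (10% and 50% also tried); 50 subjects per arm in the follow-up set; early leavers go at Week 20 (4 weeks observed) and the rest stay 14 weeks; the share r leaving early differs by arm.

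**Step 1, hazard.** h = -ln(1 - 0.30)/14 = 0.02548 per week. The 4-week risk is 1 - exp(-4h) = 9.7%; the 14-week risk is 30%.

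**Step 2, expected percentage in an arm.** p(r) = r × 9.7% + (1 - r) × 30%. For r = 0.3: 2.9% + 21.0% = 23.9%. For r = 0.7: 6.8% + 9.0% = 15.8%.

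**Step 3, chance that the test rejects at two-sided 5%.** This uses the pooled two-proportion z-test, which equals the uncorrected chi-square test. With d = p1 - p2, pooled p = (p1 + p2)/2, s0 = √[p(1 - p) × 2/50] and s1 = √[p1(1 - p1)/50 + p2(1 - p2)/50], the rejection probability is Φ[(-1.96 s0 - d)/s1] + 1 - Φ[(1.96 s0 - d)/s1]. For 30/70: d = 0.081, p = 0.198, s0 = 0.0798, s1 = 0.0794, giving 17.3%.

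| Share leaving at Week 20 (two arms) | Mean follow-up, weeks | % with AE | False-positive rate |
|---|---|---|---|
| 50 / 50 | 9 / 9 | 19.8 / 19.8 | 5.0% |
| 40 / 60 | 10 / 8 | 21.9 / 17.8 | 8.0% |
| 30 / 70 | 11 / 7 | 23.9 / 15.8 | 17.3% |
| 20 / 80 | 12 / 6 | 25.9 / 13.8 | 33.1% |

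**Step 4, range.** Over 14-week AE risks of 10% to 50%, the false-positive rate is 5.9-10.3% for 40/60, 8.8-27.0% for 30/70 and 13.7-52.8% for 20/80. The lower ends are approximate: at 10% risk the expected count is about 50 × 6.5% = 3.3 per arm, below 5, so Fisher's test would apply and would reject less often.

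**Step 5, open-ended protocol definition.** Counting all AEs in Weeks 0-30 with 100 per arm, and letting the same shares leave at Week 16 (16 weeks observed instead of 30), 30% risk gives 45.5/41.5%, 47.4/39.5% and 49.4/37.5% for the three unequal splits. The false-positive rates are 8.8%, 20.6% and 40.0%; at 50/50 it is 5.0%.

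**Step 6, rate per patient-year.** Events over observed time give 0.02548 × 52.18 = 1.33 per patient-year in both arms in every row, a ratio of 1.0. This holds by construction, because the illustration assumes a constant hazard and leaving unrelated to AE risk.

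**The case against.** **The test may not apply to follow-up AEs.** A reader might infer that the plan tests the follow-up set by chi-square. No passage says so. The test is stated for treatment-emergent AEs in general, the follow-up set appears only in the SAP, and SAP Sections 6.8.1 and 6.9.3 in places tie treatment-emergent status to the treatment period. This objection stands. What remains is that the protocol definition has no end date, the SAP does not restrict the test, and no other method is stated.

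**Unequal follow-up by arm is conjecture.** This also stands. Neither document gives transfer rates, the extension's eligibility criteria are not available, and site staff stay blinded.

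**Much is already handled.** Subjects whose last contact is the Week 16 visit are outside the follow-up set, so in that set the issue is confined to later transfers. AEs are split by period. The end-of-trial form records transfer and last visit attended, and reasons for leaving the trial are shown by treatment group. The number of AEs is tabulated as well as the percentage. None of this provides time at risk, and a raw count also depends on how long subjects are observed.

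**A rate is no cure.** Follow-up covers drug wash-out, so the hazard may change over time, and transfer driven by disease control could be informative. This is correct and limits what the rate can claim.

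**Conclusion.** The point holds as a minor gap. Time at risk in safety follow-up varies between subjects by design, the only stated between-arm AE method ignores it, and the SAP's patient-years do not reach that period. If the arms transfer alike, the crude comparison is unbiased; if they do not, it misleads even at equal AE risk.

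The range of about 8% to 33% rests wholly on assumed inputs: 30% AE risk over 14 weeks, 50 per arm, leaving at Week 20, splits from 40/60 to 20/80. It shows what could happen and does not predict this trial. The documents do not support saying that the arms will be followed for different lengths, or that follow-up AEs will certainly be tested. The primary endpoints, IGA 0/1 and EASI75 at Week 16, and treatment-period AEs are not affected by transfer.

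**What to change.** Change the SAP in three places.

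1. State that the chi-square or Fisher comparison applies to treatment-period AEs only.
2. For the safety follow-up period, present the number of AEs per patient-year by arm, with time at risk running from the start to the end of follow-up in Table 6. Keep the percentage of subjects as description, without a test.
3. Report by arm the number transferred to the extension and the median follow-up time.

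Numerator and denominator should cover the same interval. SAP Section 6.8.1 places AEs starting on the day of exposure end in follow-up, whereas Table 6 starts follow-up one second after 23:59:00 on that day; these should be aligned.

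The cost is SAP wording and a little more analysis work. The dates are already derived and no new data are needed. The rates assume a roughly constant hazard and transfer unrelated to AE risk, so they should be read as descriptive.
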